10. Are able to communicate in English.

Exclusion Criteria

Prospective participants with the following conditions will be excluded:

1. Meet DSM-IV criteria for bipolar disorder, schizophrenia, or other psychotic disorders.

2. Meet DSM-IV criteria for abuse of or dependence on any substance (other than caffeine or nicotine) in the past 60 days.
3. Have first-degree relatives (as parent or full sibling) with past or present psychiatric disorders, including schizophrenia, bipolar affective disorder and other psychoses, but excluding mood disorders.
4. Cannot have a current diagnosis of anxiety disorder that predates diagnosis with melanoma.
5. Have used psilocybin or psilocybin-containing mushrooms within the past year.
6. Require concomitant treatment with anti-psychotic medications, prescribed for the management of either psychiatric symptoms or nausea. The restriction on 5HT_{2C}/5HT₃ antagonists is applicable for 24 hours before and including the day of the study.
7. Are cachectic as indicated by loss of 10% or greater of their total weight.
8. Have been diagnosed with primary or metastatic cancer of the CNS confirmed by MRI, within 6 weeks of participation in the study.
9. Have uncontrolled hypertension.
10. Have baseline laboratory values indicative of severely compromised hepatic function, indicated by unacceptable levels of alkaline phosphatase (ALP) above 750 U/L. Participants must also have laboratory blood screening indicating ALP below 750 U/L immediately prior to administration of psilocybin.
11. Are women who are pregnant or nursing, or of child bearing potential and are not practicing an effective means of birth control.
12. Are reasonably judged to present a serious suicide or homicide risk or who are likely to require psychiatric hospitalization during the course of the study.
13. Are unable to fully understand the potential risks and benefits of the study and give informed consent.

Planned Duration of the Study

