Psilocybin given at the full dose can be expected to alter affect (mood), cognition (thought) and perception. Common side and adverse effects of psilocybin are listed in “Safety Pharmacology” in the Pharmacology section, and include anxiety, changes in

thought speed or content, depersonalization, derealization, dizziness, fatigue, inattention, impaired concentration, labile mood, nausea, paresthesias, altered time perception, altered visual perception, and unusual thoughts. Psilocybin also produces pupillary dilation and can produce changes in blood pressure and heart rate. These effects are transient and are generally gone approximately six hours after drug administration. People in previous human studies have tolerated doses of psilocybin equal to or greater than the doses employed in this study.

Like other serotonergic psychedelics, psilocybin can produce a number of psychological adverse events, most of them related to increased anxiety or psychological distress. The likelihood of these effects occurring during a controlled study is far lower than during nonmedical use (Halpern and Pope 1999; Hasler et al. 2004). However, the investigators will whenever possible take the steps below to further reduce or prevent their occurrence.

Panic attacks, severe generalized anxiety, or persisting insomnia

Psilocybin can produce anxiety and/or panic response, and less commonly, a prolonged unpleasant experience (or “bad trip”), as can other serotonergic psychedelics, such as LSD. Medical case reports and case series specific to consumption of psychedelic mushrooms (Hyde et al. 1978; Musha et al. 1986; Peden and Pringle 1982) report that emergency department admissions after use of psilocybin-containing mushrooms report transient anxiety or panic. The most commonly reported adverse events described in a survey of 44 individuals admitted to hospital after psilocybin use were dysphoria that lasted for an average of 3.8 hours, followed by nausea or vomiting, occurring in almost half the admissions (Peden and Pringle 1982).

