As is true of the pharmacologically similar compound LSD, psilocybin use is associated with transient and sometimes prolonged psychotic states in users (Benjamin 1979; Halpern and Pope 1999). Researchers who reviewed case series and reports that associated LSD or serotonergic psychedelics more generally with subsequent occurrence of psychosis note that diagnosis of psychosis is made only after drug use, and not prior to it (Strassman 1984). After examining the literature, Strassman concluded that LSD might trigger psychotic episodes in people already vulnerable to psychosis but that it did not directly cause psychosis in people not susceptible to it. Two large studies surveyed clinicians or researchers who had conducted LSD research or LSD-assisted psychotherapy (Cohen 1960; Malleson 1971) and found the prevalence of psychiatric symptoms after participation to be very low. None of the participants in recent psilocybin studies experienced psychotic states, though some participants exhibited transient paranoia or some loss of insight into the situation during the course of psilocybin effects (Gouzoulis-Mayfrank et al. 1999b; Griffiths et al. 2006; Vollenweider et al. 1997). These findings suggest that while psilocybin can provoke psychosis or other psychiatric symptoms in a very small percentage of people, it does not do so often, and that receiving a psychedelic drug as part of a research study is extremely unlikely to trigger transient or persistent psychosis. The occurrence of transient or persistent psychosis can be prevented or further reduced by screening subjects on the basis of past and current mental health. Subjects with a personal or family history in first-degree relatives of psychosis (bipolar disorder or schizophrenia), or suicide attempts will be excluded from this study.

If a participant should become psychotic or suicidal for a time exceeding the duration of drug effects and the investigators are unable to ameliorate these symptoms, arrangements will be made for him or her to be admitted to the nearest inpatient psychiatric facility at the clinic.

Chronic neuropsychological effects

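### Exclusion criterion 3 (family psychiatric history) contradicts itself on bipolar disorder and does not match the protocol's own restatement of the rule in its risk section

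*Protocol*

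**What the plan says.** Three places in the protocol bear on the psychosis screen.

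- **Exclusion Criteria, item 3** covers relatives. It begins "Have first-degree relatives (as parent or full sibling") and continues "with past or present psychiatric disorders, including schizophrenia, bipolar affective disorder and other psychoses, but excluding mood disorders".
- **Exclusion Criteria, item 1** covers the candidate's own diagnosis: "Meet DSM-IV criteria for bipolar disorder, schizophrenia, or other psychotic disorders". It has no exemption for mood disorders.
- **Psychosis, suicidal thoughts or impulses** (in the risk section) says that psychosis "can be prevented or further reduced by screening subjects on the basis of past and current mental health". It then restates the rule for people with a personal or "family history in first-degree relatives of psychosis (bipolar disorder or schizophrenia), or suicide attempts will be excluded from this study".

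The only numbered criterion on suicide is item 12, which applies to candidates who "Are reasonably judged to present a serious suicide or homicide risk" or are likely to need psychiatric admission during the study.

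**The concern.** A family-history criterion should give a screener one answer for each candidate. Item 3 falls short of that in two ways, and the risk section adds a third difficulty.

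First, item 3 lists bipolar affective disorder among the disorders that exclude and ends by exempting mood disorders, with no word such as *other* to keep bipolar disorder out of the exemption. Second, its class is psychiatric disorders in general. The named psychoses are given only as examples, and only mood disorders are taken out. Third, the risk section describes a different class for the same purpose and adds suicide attempts.

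The protocol relies on this screening as a means of preventing drug-related psychosis. The criteria are also applied more than once. Under Method, active-placebo participants are re-screened before open-label dosing, and the Visit 5 form in Appendix B asks again whether all criteria are still met. A rule that depends on which section the screener has open can admit or refuse the same person.

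**Working it through.** There is no figure to reproduce: the point rests on wording, and no sample size, power or error rate enters it. The check sets the two statements of the rule side by side for five kinds of history.

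| History | Exclusion Criteria | Risk section | Result |
|---|---|---|---|
| 1. Relative with schizophrenia | Excluded (item 3) | Excluded | Agree |
| 2. Relative with bipolar disorder | Named as excluding, but also within the exempted class (item 3) | Excluded | Item 3 conflicts with itself |
| 3. Relative with unipolar depression | Exempt (item 3) | Not listed | Agree |
| 4. Relative with a non-mood, non-psychotic disorder (anxiety disorder, OCD, PTSD, alcohol dependence) | Excluded by the open wording (item 3) | Not listed | Differ |
| 5. Past suicide attempt | Not listed; item 12 concerns currently judged risk | Excluded | Differ |

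*Case 2.* That bipolar affective disorder is a mood disorder follows from the protocol's own vocabulary. Under Risk of the Experimental Drug it writes "Psilocybin given at the full dose can be expected to alter affect (mood"), treating affect and mood as the same thing. The intent can still be recovered. Item 3 itself places bipolar disorder beside other psychoses, item 1 groups it with psychotic disorders, and the risk section lists it as excluding with no exemption. No passage says that a bipolar relative is acceptable.

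*Case 4.* Intent does not settle this one. The exemption of mood disorders suggests that the class was meant to be wider than psychosis, while the risk section suggests that psychosis was the target. The literal reading also sits oddly with the rest of the list. Item 2 bars the candidate's own substance abuse or dependence only if it falls within the past 60 days, yet a parent's alcohol disorder at any time would bar the candidate under item 3. Inclusion criterion 2 selects for anxiety, yet a sibling's anxiety disorder would exclude. The protocol gives no safety reason for either result.

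*Case 5.* Here the risk section is the broader text. Its sentence also leaves unclear whether attempts by relatives count or only the candidate's own. The section on Acute Psychological Distress provides for withdrawal on suicidal ideation or intent, which again is not a history of attempts.

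So neither text contains the other: the criteria are wider in case 4 and the risk section is wider in case 5.

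*Scale.* The study is to have nine completers, so one decision that turns on which passage was followed concerns 1/9 = 11.1% of the sample.

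**The case against.** The strongest reply is that the one case with a direct bearing on psychosis, the bipolar relative, is answered by the protocol itself. Item 3 names the condition, the risk section names it again, and the natural reading is that the exemption covers other mood disorders. That stands. A reader might infer that item 3 has no settled meaning at all, or that it lets a candidate with a bipolar parent be dosed. The documents do not support either, because a screener would have to disregard an express listing in two places.

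A reader might also infer that the protocol's main defence against psychosis is broken. That goes too far. Item 3 is only the family-history part. The candidate's own status is covered by item 1, which is clear, by the SCID at baseline, and by item 6 on anti-psychotic medication.

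It can further be said that the risk section is narrative: it says that people with a family history of psychosis are excluded, not that only they are. A wider criterion is compatible with it and errs towards exclusion. This has some force, and it makes case 4 mainly a question of recruitment and consistency. It does not remove the difficulty, because the criterion taken alone gives results for which the protocol offers no reason, and a screener who departs from the literal text has no guide to how far to go. The reply also fails in the other direction: the risk section says outright that suicide attempts exclude, and someone working from the numbered list would not apply that.

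**Conclusion.** The point holds as a contradiction in a safety-related eligibility rule. Item 3 is inconsistent on bipolar disorder, with a likely intent that other passages reveal but its own wording does not state cleanly. Its open class does not match the risk section for relatives with non-mood, non-psychotic disorders. The risk section's exclusion for suicide attempts has no counterpart among the numbered criteria.

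The consequence is confined to who may be enrolled and dosed. The protocol gives no prevalence of such histories among candidates, so the number affected cannot be estimated from it, and the conclusion does not depend on one. It rests on reading the sentences as printed and on the protocol's equation of affect with mood. Eligibility is fixed in the protocol, so a statistical analysis plan could not resolve this. It should be corrected before screening continues.

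**What to change.** Replace the open wording of item 3 with a closed list of the diagnoses in first-degree relatives that exclude. State expressly how the mood-disorder exemption applies to bipolar disorder. Settle whether a history of suicide attempts excludes and, if so, whether it is the candidate's own, a relative's or both. Then either give it a numbered criterion or remove it from the risk section. Use the same list under Exclusion Criteria, under Psychosis, suicidal thoughts or impulses, and on the eligibility form. Which histories belong on the list is for the clinical team to decide; the statistical request is only that the passages be reconciled so that one candidate gets one answer.

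The cost is about one line in each of the two sections and on the form, within a single amendment. No analysis, sample size or visit schedule changes.

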The active placebo in this study will be a low dose of the investigational drug. Active placebo dose of psilocybin was chosen on the basis of early and recent studies of psilocybin in humans (Hasler et al. 2004; Isbell 1959; Moreno et al. 2006; Passie et al. 2002). This dose was chosen for its ability to produce a few of the effects of psilocybin without producing any of the potentially therapeutic effects. People may perceive lights or colors as being brighter and sounds as being different, and they may experience slight changes in mood, cognition or perception. A 4 mg dose of psilocybin is not expected to generate a mystical or transformative experience.

Sample Population and Subjects

The study will enroll nine (9) individuals with the following criteria listed below. Study drop-outs or withdrawals will be replaced until nine participants have completed the randomized phase of the study. Study completion will be defined as attending visits from screening up through the follow-up two weeks after the second psilocybin-assisted session. Participants who are unable to complete or withdraw from the open-label phase or before the two-month follow-up phase will not be replaced. Inclusion Criteria

Inclusion Criteria

Prospective participants must meet the following inclusion criteria listed below to be eligible for study enrollment.

1. Have been diagnosed with Stage IV melanoma with a life expectancy of one year or less
2. Meet diagnostic criteria for anxiety on the SCID, or a score of 8 or higher on the HADS Anxiety score.
3. Diagnosis must be a new diagnosis of anxiety subsequent to diagnosis with melanoma.
4. Are 18 years or older,
5. Live with another adult who is their primary caregiver, who can also provide transportation to and from the cancer center for each experimental session and who also consents to take part in a parallel investigation of anxiety and depression in primary caregivers. The same caregiver may remain overnight with participants after each psilocybin session.
6. Have a Mini-Mental State Exam score of 27 or higher.
7. Are willing to commit to medication dosing, experimental sessions with overnight stay, traveling to follow-up sessions, and to complete the evaluation instruments.
8. Are willing to refrain from taking any anti-depressants during the study period.
9. Are willing to refrain from taking any benzodiazepines during the 24 hours preceding each scheduled psilocybin, placebo, or open label session.

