The therapist-investigators will conduct at least one introductory psychotherapy session no later than seven days after the baseline evaluation. Introductory sessions will provide up to six hours of preparation, including one to two sessions of psychotherapy that will last from 90 to 120 minutes, and working with a hypnotic induction CD. Introductory sessions may be presented by one or both of the investigator-therapists. Introductory psychotherapy will occur after participants are assessed for continued study eligibility and complete measures of anxiety and depression.

After introductions are shared between the participant and the therapist-investigators, at least one and possibly both of the investigators will discuss the participant's lifespan and psychological development, any goals or desires they have, their spiritual beliefs or world-view and any beliefs about death or the afterlife, and any past experiences that share some similarities with psilocybin-assisted psychotherapy, such as any past use of classical hallucinogens/psychedelics and any past mystical or transformative experiences. The therapist-investigators will teach mindfulness techniques, such as diaphragmatic breathing with cognitive-behavioral stress management in a spiritual context. The therapist-investigators will inform participants of what to expect during a psilocybin-assisted psychotherapy session and they will address any specific hopes, fears or specific goals the participant has in respect to the upcoming psilocybin-assisted psychotherapy sessions. The investigators will also provide participants with a CD containing procedures for hypnotic induction, and if there is time available, one or both therapist-investigators will review and discuss the content of the hypnotic induction CD. The investigators will present participants with instructions and food, alcohol or medication restrictions for the time starting 24 hours prior to a psilocybin-assisted psychotherapy session, and the participant will be encouraged to ask questions about these instructions. A second introductory session will occur if the investigators deem it necessary. The investigators will meet with any significant other who plans to accompany the participant for part of a psilocybin-assisted session and the overnight stay, if applicable.

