- **Introductory Psychotherapy (Visits 4-4.5):** Two 90 to 120-minute introductory psychotherapy sessions. The participant will complete measures of anxiety and depression (HADS, STAI), spirituality and quality of life (FACIT-Sp and EORTC-QLQ-C15). Psychotherapy takes place with both investigator-therapists following assessment, with a particular emphasis on the participants' chief religious and spiritual beliefs, as well as existential concerns. Introductory sessions will be recorded to audio and video, and participants will have an opportunity to review the recordings. The investigators will provide participants with instructions on mindfulness and self-hypnosis, and they will provide participants with a self-hypnosis CD during one introductory session. If there are two introductory sessions, participants will complete anxiety measures prior to the first introductory session and the spirituality and quality of life measures in the second session. Participants will also receive instructions and restrictions relating to food and drug consumption for the night before and morning of the psilocybin-assisted session.
- **Psilocybin-Assisted Psychotherapy Session 1 (Visit 5):** First day-long psilocybin-assisted psychotherapy session. On arrival, the participant will undergo blood draw for assessing liver function, assessment of mental competency through MMSE and urinary drug and pregnancy screen, with positive tests from these tests resulting in either delaying or rescheduling the session to withdrawal from the study. The participant will next complete measures of anxiety and depression (HADS, STAI), spirituality (FACIT-Sp) and quality of life (EORTC-QLQ-C15). The session will be recorded to audio and video, and participants will have an opportunity to review the recordings. After these measures are completed, a capsule of 4 or 25 mg psilocybin will be administered, and the participant will be encouraged to sit or lie comfortably for the duration of the session. Blood pressure will be measured immediately

before, and hourly for the first three hours. The investigators will remain with the participant for up to six hours later or until drug effects have waned. A significant other may stay with the participant during part of the therapy. All participants will remain overnight.

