All prescription concomitant medications will be recorded at baseline. During the study participants will keep a daily log of medications taken while actively enrolled in the study protocol. Only changes to anxiolytic and pain management baseline medications will be recorded on the CRF.

Laboratory Assessments

Before the study, the investigator will supply the sponsor with a list of the normal ranges for clinical laboratory assessments. All abnormal laboratory values require a comment from the investigator on the laboratory report, regardless of the clinical significance.

After reviewing the laboratory report and evaluating any results that are outside the normal range, the investigator must sign and date the laboratory report. Any abnormal laboratory test result that warrants further investigation to guard the subject's safety will be repeated as appropriate and reviewed by the investigator.

Study Monitoring, Auditing and Documentation

Investigators and/or their study staff will be trained during the initiation visit. During each monitoring visit, source data verification will be performed by qualified staff representing the sponsor. A CRF collation supplied by the sponsor will be completed for each subject. The entries will be checked by trained delegates of the sponsor.

Monitoring and auditing procedures of the sponsor will be followed, in order to comply with GCP guidelines and to ensure validity of the study data.

The sponsor will review the study documentation used for planning, conduct and monitoring of the study in order to ensure compliance with GCP and local regulations. This documentation includes as a minimum: the Investigator's Brochure, the Study Protocol, the Case Report Forms and the Subject Information and Consent Form.

Risks to Participants

Risks and Discomforts Related to Screening and Baseline Examination

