There is scant literature on potential drug-drug interactions between psilocybin and other medications or psychoactives, and a review addressing the pharmacology of psilocybin fails to mention any interactions of note (Passie et al. 2002). Research studies in humans demonstrated that drugs that antagonize the 5HT_{2A} receptor may attenuate or eliminate most of the subjective effects of psilocybin, very likely including therapeutic effects (Carter et al. 2007; Vollenweider et al. 1998) and that D₂ receptor antagonists, as haloperidol, attenuate effects on positive mood and increased anxiety (Vollenweider et al. 1998). Surveys of recreational users of serotonergic psychedelics, including psilocybin, suggests that selective serotonin uptake inhibitors (SSRIs) may at first enhance psychedelic effects, but that chronic SSRI treatment attenuates drug effects, and that treatment with MAOIs also attenuates the effects of LSD in humans (Bonson et al. 1996).

By contrast, a chronic course of tricyclic antidepressants may amplify the psychedelic effects of serotonergic psychedelics, likely including psilocybin (Bonson and Murphy 1996).

Early research in rats found that opioid agonists attenuated LSD-associated behavior in rats, such as changes in body posture and disruption of operant conditioning for food reward, while opioid antagonists enhanced these behaviors (Domino 1986; Ruffing and Domino 1981). As noted in “Drug Description and Dose” above, [name], the principal investigator conducting the study of psilocybin-assisted psychotherapy in people with advanced stage cancer, reported that opiates attenuated the effects of psilocybin, but otherwise produced no adverse drug-drug interactions (Grob 2007). This pilot study of psilocybin-assisted psychotherapy may contribute to knowledge of the safety of psilocybin in a medical setting, but based on the existing literature, we are taking appropriate cautions.

Abuse Liability

Currently psilocybin has been placed in the most restrictive schedule of drugs in the US (Schedule 1), defined as having no medical use and having high abuse liability. Despite this designation, examining use patterns in humans and self-administration and conditioned aversion in nonhuman primates suggest that psilocybin possesses little abuse potential. See the section on drug dependence and abuse potential in “Additional Information” for research findings on abuse potential and self-administration of psilocybin.

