Research conducted during the 1950s and 1960s found that psilocybin, like LSD, can be used in combination with psychotherapy (Passie 2005; see for example (Fontana 1961; Leary et al. 1963). Therapists used some of the subjective effects of these serotonergic hallucinogens to stimulate or uncover unconscious feelings or memories and to facilitate breaks with routine or habitual behavior. In the psychotherapy context, potentially therapeutic effects of psilocybin include changes in ego boundary, stimulating unusual thoughts and views of the self and the world, and mood lability. From a traditional psychodynamic viewpoint, a less rigid or more expanded ego boundary and viewing the self or the world in a new perspective can offer a chance for insight, and profound changes in mood and can facilitate confrontation with these emotions. Furthermore, psychotherapy utilizing serotonergic hallucinogens consistently contained spiritual elements which in and of themselves seemed to have profound, positive effects on patients (Griffiths et al. 2006; Pahnke 1963). All three combined may help produce mystical or transformative experiences. These effects of psilocybin may help reduce anxiety when experienced in a safe and supportive environment. However, none of these early studies sought to examine the pharmacological bases of these effects, and to date, there are still no studies that tie a specific putative therapeutic effect of psilocybin with a specific pharmacological action. All serotonergic hallucinogens appear to share activity at 5HT_{2A} receptors, suggesting that these receptors are necessary, but not sufficient, for producing alterations in affect, cognition and perception (Nichols 2004). Psilocybin exhibits an affinity for 5HT_{2A} receptors (McKenna et al. 1990) and it has a stronger affinity for human than rat 5HT_{2A} receptors (Gallaher et al. 1993). Administration of the 5HT_{2A}/5HT_{2C} antagonist ketanserin attenuated subjective effects of psilocybin (Vollenweider et al. 1998) and reduced psilocybin effects on visual perception (Carter et al. 2005a). It is possible that psilocybin alters consciousness through compound-specific alterations in secondary messenger signaling upon activating 5HT_{2A} receptors (“allosteric receptor trafficking”), as both psilocybin and LSD stimulate the arachidonic acid pathway when activating rat 5HT_{2A} receptors (Kurrasch-Orbaugh et al. 2003). While a study chiefly comparing LSD with the non-hallucinogenic compound lisuride in mice suggests that serotonergic hallucinogens produce at least some of their subjective effects through selective stimulation of secondary messengers, researchers have not examined psilocybin in similar studies. Finally, it is possible that some of the potentially therapeutic effects of psilocybin are the result of changes in gene expression stimulated by 5HT_{2A} receptor activation (Gonzalez-Maeso et al. 2003; Nichols and Sanders-Bush 2002). It is not clear

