
what significance these changes in gene expression have on the generation of subjective effects.

Table 1

Psilocybin Binding Data

Receptor	Ki (nM)	Hot Ligand	Species	Source	Reference
5HT1A	190	3H-8-OH-DPAT			
5HT2A	6	3H-DOI	Rat/cow	Brain	(McKenna et al. 1990)
5HT2C	410	3H-Ketanserin	Rat/cow	Brain	(McKenna et al. 1990)

Table 2

Psilocin binding Data

Receptor	Ki (nM)	Hot Ligand	Species	Source	Reference
5-HT1A	49	3H-8-OH-DPAT	Human	Cloned	(Blair et al. 2000)
5-HT2A	25	125I-DOI	Rat or bovine	Cloned	(Blair et al. 2000)
5-HT2C	10	125I-DOI	Rat	Cloned	(Blair et al. 2000)

Some neuroscientists hypothesize that serotonin 5HT_{1A} and 5HT_{2C} receptors play a role in producing at least some and perhaps most of the effects of serotonergic hallucinogens (Nichols 2004). It is notable that most 5HT_{2A} agonists also act on 5HT_{2C} receptors, making it difficult to single out only one of the two receptors as key for producing the effects of psychedelics. To date, work has not specifically studied the effects of psilocybin or psilocin on 5HT_{2C} receptors. Psilocybin activates 5HT_{1A} receptors. Direct application of psilocybin to dorsal raphe nucleus (DRN) neurons reduces firing of DRN neurons (Aghajanian et al. 1968; Aghajanian and Hailgler 1975), an effect attributed to 5HT_{1A} activity. Administering the 5HT_{2A/2C} antagonist ketanserin along with psilocybin reduced most psychedelic effects in humans without reducing self-reported fatigue or inattention, and without preventing psilocybin from altering binocular rivalry (Carter et al. 2005b), findings suggesting that 5HT_{1A} receptor activation may produce or modulate some, but not all, psilocybin effects.

Previous research has reported that LSD produced analgesia that outlasted its subjective effects (Kast 1966). It is possible that psilocybin shares this effect with the related serotonergic hallucinogen. The pharmacological mechanisms for LSD-induced analgesia remain unclear, and researchers do not know if psilocybin produces analgesia. If LSD causes analgesia as a result of activating 5HT₂ or 5HT_{1A} receptors, then psilocybin may share these effects as well.

Secondary Pharmacology

Safety Pharmacology

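### Exclusion 6 restricts 5HT2C and 5HT3 antagonists before dosing but does not name 5HT2A antagonists, the class the protocol's own interaction section singles out (minor correction)

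*Protocol*

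**What the plan says.** Exclusion Criteria, item 6, has two sentences. The first excludes people who need antipsychotic medication, whether for psychiatric symptoms or for nausea, with no time limit. The second says that the restriction on 5HT2C/5HT3 "antagonists is applicable for 24 hours before and including the day of the study". No such restriction is set out anywhere else in the Protocol.

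The pharmacology is described in two places:

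- Potential for Drug/Drug Interactions: drugs that antagonize the 5HT2A "receptor may attenuate or eliminate most of the subjective effects of psilocybin, very likely including therapeutic effects".
- Drug Activity Related to Proposed Action: action at 5HT2A is presented as common to psilocybin's whole drug class, "suggesting that these receptors are necessary, but not sufficient, for producing alterations in affect, cognition and perception". The same section reports a hypothesis that 5HT1A and 5HT2C "receptors play a role in producing at least some and perhaps most of the effects of serotonergic hallucinogens".

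The other medication rules are these:

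- Inclusion 8 bars antidepressants for the study period.
- Inclusion 9 bars benzodiazepines "during the 24 hours preceding each scheduled psilocybin, placebo, or open label session".
- At the introductory session, participants are told of "food, alcohol or medication restrictions for the time starting 24 hours prior to a psilocybin-assisted psychotherapy session". The visit-by-visit summary describes "instructions and restrictions relating to food and drug consumption for the night before and morning of the psilocybin-assisted session". Neither text names a drug class.
- Under Collection of Concomitant Medications, "All prescription concomitant medications will be recorded at baseline", and participants keep a daily medication log.

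**The concern.** A pre-dose medication rule in this trial has to keep the 25 mg dose pharmacologically active. If a full-dose participant takes a drug that blocks the effect, that participant may respond more like someone given 4 mg. Both the between-arm contrast and the planned analyses of the mystical-experience measure then lose meaning.

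The one receptor-based rule in the eligibility criteria does not name the receptor whose blockade the Protocol says may remove the effect. It does name 5HT3, for which the Protocol describes no interaction with psilocybin. Eligibility belongs in the protocol, so this is not a detail that an analysis plan would supply.

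**Working it through.** No figure in the Protocol depends on this sentence, so the check is a comparison of texts.

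**Step 1: which 5HT2A-blocking drugs does each rule catch?**

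| Type of drug | Caught by | Time limit |
|---|---|---|
| Required antipsychotic, including for nausea | Exclusion 6, first sentence | None stated |
| Antidepressant | Inclusion 8 | Whole study |
| Mixed 5HT2A/5HT2C antagonist, such as ketanserin | Exclusion 6, second sentence, through its 5HT2C action | 24 hours before, and the day |
| 5HT2A antagonist with no 5HT2C or 5HT3 action, neither antipsychotic nor antidepressant | No rule | Not applicable |

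The third row is probable, not certain. The pharmacology section uses the slash form 5HT2A/5HT2C for one agent that blocks both receptors. Read the same way, 5HT2C/5HT3 in exclusion 6 would cover only agents that block both of those receptors, and ketanserin would not clearly be caught. The more natural reading is either class.

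**Step 2: would the remaining checks stop a drug in the last row?** The baseline medication record, the daily log, the diary's reminder to call before starting an unreviewed drug (Appendix A) and the form for new psychotropic medication (Appendix B) can bring the drug to notice. They do not say that it is barred. The Visit 5 form in Appendix B asks whether the participant still meets every inclusion and no exclusion criterion. For a drug in the last row, the criteria as written do not give a reason to answer no.

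**Step 3: the window.** Exclusion 6 refers to the day of the study, which is best read as the dosing day. Inclusion 9 states its window properly, by session. The same form would remove the doubt.

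**Step 4: reach of the rule.** Counting nine completers and ignoring replacements:

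- Randomized sessions: 9 × 2 = 18, of which 6 × 2 = 12 are at 25 mg and 3 × 2 = 6 are at 4 mg.
- Open-label sessions: at most 3 × 2 = 6, all at 25 mg.
- Total: at most 18 + 6 = 24, of which 12 + 6 = 18 are at 25 mg.

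This is the number of sessions that the sentence governs. It is not an estimate of how many could be affected.

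**The case against.** The strongest reply is that nothing practical is missing. The only 5HT2A antagonist that the Protocol names is ketanserin, which it describes as a mixed 5HT2A/5HT2C agent, so the 5HT2C wording already reaches the evidence cited. What remains is a drug that blocks 5HT2A, has no 5HT2C action, is neither an antipsychotic nor an antidepressant, and would plausibly be taken by a patient with stage IV melanoma. The documents do not show that such a drug exists. Several layers of medication recording and instruction also stand between it and a dosing session.

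Most of this stands, and it limits the size of the point. It does not remove the mismatch: the interaction section speaks of a class, the criterion names other classes, and coverage of mixed agents depends on how the slash is read.

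Two objections to a remedy also have force. The documents give no washout data for any antagonist, so 24 hours is simply the Protocol's existing window carried over. And a timed sentence naming 5HT2A could be read as allowing an antipsychotic or antidepressant up to the day before dosing, unless it says otherwise.

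Three stronger readings are tempting, and the documents do not support them:

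- A reader might infer that the full-dose arm will be diluted. No use of such a drug is documented, and the Protocol says only that these drugs may attenuate or eliminate effects.
- A reader might infer that 5HT2C is a misprint for 5HT2A and should be replaced. The text does not settle what was intended, and 5HT2C has a stated, if hypothetical, basis, so it should stay.
- A reader might infer that the two descriptions of the pre-session instructions conflict. The second is a brief visit summary and does not cancel the 24-hour start in the first.

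**Conclusion.** The point holds as a minor correction. Exclusion 6 omits the antagonist class that the Protocol itself says may remove psilocybin's subjective and very likely therapeutic effects, and its window is loosely worded.

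The consequence is small and cannot be quantified, because the documents do not say whether any participant would take a drug that falls in the gap. The conclusion that the gap is narrow rests on two assumptions: that the antipsychotic and antidepressant bars are applied as written, and that 5HT2C/5HT3 means either class. Nothing here shows an effect on the primary analysis, on power or on safety.

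**What to change.** Leave the first sentence of exclusion 6 and inclusion 8 unchanged. Replace the second sentence of exclusion 6 with:

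*In addition, and without relaxing the exclusion of required antipsychotics or the bar on antidepressants, any antagonist of 5HT2A, 5HT2C or 5HT3 receptors must not be taken for at least 24 hours before, or on the day of, each psilocybin session (Visits 5, 8, 13 and 16).*

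Check it at the session-day eligibility review. The sample form covers Visit 5, and Appendix B says that visits seven to ten will record nearly the same information, which takes in Visit 8. The same check should be used at Visits 13 and 16.

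The cost is an amendment of one sentence, with no new type of form. The existing 5HT3 limit is kept and no antiemetic class is added by name. The downside is an occasional rescheduled session, with the second session still to fall 7 to 14 days after the first.
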